8.3.3 Laboratory Assessments

Routine safety laboratory tests (complete blood count/differential, urinalysis, and serum chemistry) will be performed as per the SoA ([Table 1](#)) and Appendix [17.1](#). Any out-of-range laboratory result that is considered clinically significant by the Investigator will be recorded as an AE and should be confirmed by repeat testing at the discretion of the Investigator. Clinically significant laboratory abnormalities at any visit will be followed to resolution (return to normal or to the Baseline state) or until clinically stable as determined by the Investigator until the study database is closed.

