11 SAFETY INSTRUCTIONS AND GUIDANCE

11.1 Adverse Events

11.1.1 Definition of Adverse Event

An AE is any untoward medical occurrence in a subject administered a medicinal product and which does not necessarily have a causal relationship with the medicinal (investigational) product. AEs include any unfavorable and unintended illness, sign (e.g., including an abnormal laboratory finding), symptom, clinically significant laboratory test abnormality, or disease associated with the use of a medicinal (investigational) product that has appeared or worsened during the course of the clinical trial, regardless of causal relationship to the medicinal (investigational) product under study.

Subjects will be questioned about any concurrent illness or systemic sign or symptom. Any incidence of these systemic signs or symptoms will be reported on the AE eCRF.

Vital signs and laboratory abnormalities are to be recorded as AEs only if they are clinically significant (for example: are symptomatic, requiring corrective treatment, leading to discontinuation or fulfilling a seriousness criterion). A laboratory abnormality that is part of an efficacy endpoint (e.g., histologic confirmation of BCC on a biopsy) is not to be reported as an AE.

An unexpected AE is one that is not listed in the Investigator's Brochure (IB) or is not listed at the specificity or severity that has been observed.

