11.1.2 Documenting Adverse Events

It is the responsibility of the Investigator to document in the eCRF all AEs/SAEs that occur during the course of the study. AEs/SAEs should be collected after the informed consent form is signed and usually at the Screening visit. The AEs/SAEs should be documented as a single medical diagnosis. When this is not possible, the AE/SAEs should be documented in terms of signs and/or symptoms observed by the Investigator or reported by the subject at each study visit.

All AEs/SAEs occurring after the subject signs the informed consent through the last study visit must be reported, regardless of whether or not the AEs/SAEs are considered drug-related. All AEs/SAEs, whether in response to a query, observed by the study site personnel, or reported spontaneously by the subject, will be recorded.

At each visit during the study, the subject will be assessed for the occurrence of new and ongoing AEs. Dermal safety and tolerability that result in the subject requiring a concomitant therapy or discontinuation from the study will be reported as an AE/SAE. The following data will be collected on all AEs and recorded on the appropriate eCRF:

- Event name (diagnosis preferred, if unknown, record the signs/symptoms)

- Onset date and end date
- Maximum severity
- Seriousness
- Action taken regarding IP
- Corrective treatment, if given
- Outcome

In addition, the Investigator's assessment of causality will be recorded

It is not necessary to capture multiple occurrences of an AE separately if the event recurs at short intervals. In such instances the end date of the AE is the date when the event resolved last and did not recur. If however the event recurs after long intervals, then the subsequent event may be captured as a separate event. The PI may use his discretion to determine what constitutes a long or short interval between events and which event is reported once versus more than once. Furthermore, protocol defined end points (e.g new BCCs on the face, nSEBs on the face and BCC surgeries on the face) will be summarized as efficacy parameters and are not to be reported as AEs/SAEs.

In the clinical database, all AEs including SAEs are to be followed for a minimum up to the 30 day follow up visit. In the source documents, any and all AEs including SAEs must be thoroughly documented to conclusion or in the opinion of the investigator, the event has resolved or stabilized.

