12.7.4 Safety Laboratory Values

Changes from Baseline in safety laboratory values will be summarized with descriptive statistics for each treatment group at all applicable study visits.

Shift tables will be presented for changes in safety laboratory values to summarize laboratory test results collected at Screening to Baseline (Day 1) and at Months 1, 3, 6, 9, and Month 12/Exit Visit. Normal ranges established by the local laboratory will be used to determine the shifts. A listing of all out-of-range laboratory test results at any assessment

time point will also be provided. Determination of clinical significance for all out-of-range laboratory values will be made by each Investigator and reported as an AE accordingly. In addition, a listing of all clinically significant laboratory test results will be provided.

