2. STATISTICAL METHODOLOGY

2.1 General Principles

Continuous parameters will be summarized by number of non-missing observations (n), mean, standard deviation (SD), median, minimum, and maximum (with the exception of laboratory and vital sign parameters which will be summarized by mean, SD, and median). Categorical parameters will be summarized by count and percentage of the non-missing responses. All statistical analyses will be performed using SAS® Version 9.4 or later. AEs and medical history will be coded using the Medical Dictionary for Regulatory Activities (MedDRA) version 21.1 or later. Prior and concomitant medications and procedures/therapies will be coded using the World Health Organization (WHO) Drug Dictionary version Global B3 01SEP2018 or later.

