Changes from Baseline to last on treatment in safety laboratory values, including chemistry and hematology, will be summarized separately with descriptive statistics in SI units for each treatment group at all applicable study visits. Separate listings for each panel will be provided.

Shift tables will be presented for changes in safety laboratory values to summarize laboratory test results from baseline to last on treatment. Normal ranges established by each of the central laboratories will be used to determine the shifts. A listing of all out-of-range laboratory test results at any assessment time point will also be provided. Determination of clinical significance for all out-of-range laboratory values, derived as any AE with a system organ class of Investigations, will be made by each Investigator and included in the listing. In addition, a listing of all clinically significant laboratory test results will be provided.

Pregnancy and urinalysis results will be provided in listings. A shift table for urinalysis results (normal vs. abnormal) from baseline to last on treatment will be provided.

Physical Examinations

Changes from Baseline for last on treatment in vital sign measurements will be summarized with descriptive statistics for each treatment group. A listing of vital signs results will be provided.

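### The SAP flags laboratory values as clinically significant only through AEs coded to SOC Investigations, so AEs recorded as a diagnosis may go unflagged

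*SAP*

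**What the plan says.** SAP 2.6, under Safety Laboratory Tests, describes a listing of all out-of-range results. It says each Investigator determines clinical significance and that this determination will be shown in the listing. The same sentence defines how the determination is obtained: "derived as any AE with a system organ class of Investigations". The next sentence adds that "a listing of all clinically significant laboratory test results will be provided". The SAP names no other source for the flag.

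The protocol treats the matter in four places:

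- Section 8.3.3: "Any out-of-range laboratory result that is considered clinically significant by the Investigator will be recorded as an AE".
- Section 12.7.4: "Determination of clinical significance for all out-of-range laboratory values will be made by each Investigator and reported as an AE accordingly". This section also promises the listing of clinically significant results.
- Section 11.1.1: "Vital signs and laboratory abnormalities are to be recorded as AEs only if they are clinically significant".
- Section 11.1.2, on how any AE is to be named: "The AEs/SAEs should be documented as a single medical diagnosis". Signs and symptoms are the fallback, and the list of eCRF items repeats that a diagnosis is preferred.

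None of these limits clinically significant laboratory results to one SOC. The SOC comes from coding: SAP 2.1 states that "AEs and medical history will be coded using the Medical Dictionary for Regulatory Activities (MedDRA) version 21.1 or later". SAP section 4, which lists departures from the protocol, mentions a change to the laboratory summaries but not this derivation.

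**The concern.** Using AEs to carry the Investigator's judgement fits the protocol. The difficulty is the SOC filter placed on top. The Investigator supplies the wording of the event, and the coding dictionary supplies the SOC. A filter on SOC therefore selects by how the event was worded, not by whether the Investigator judged the result significant. It keeps events worded as a test finding and can drop events worded as a diagnosis, which is the form that Protocol 11.1.2 prefers.

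At stake is one safety output and one flag. A listing presented as containing all clinically significant laboratory results could be incomplete. The results left out could be ones serious enough to have been given a disease name. A reader of the study report could not tell this from the listing itself.

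**Working it through.** No figure in the plan bears on this point, so the check is a comparison of text.

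1. **What the protocol defines.** Sections 8.3.3 and 12.7.4 give a set of results that are out of range, judged clinically significant by the Investigator and recorded as AEs. Call this set P. SOC plays no part in it.

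2. **What the SAP derives.** Section 2.6 takes AEs whose SOC is Investigations. Call this set S. It is the only stated route to the flag. The SAP describes no significance field on the laboratory form, no list of preferred terms and no link from an AE to a laboratory record.

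3. **In P but not in S.** Protocol 11.1.2 asks for a diagnosis first. Assume that a laboratory-related diagnosis is generally coded to the organ system of that diagnosis. Its AE then lies outside S, the result is not flagged, and it does not reach the listing. The examples of clinical significance in Protocol 11.1.1 (symptoms, corrective treatment, discontinuation, seriousness) describe cases that a site could readily name as a diagnosis.

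4. **In S but not in P.** Under Protocol 8.3.2 and 11.1.1, clinically significant vital-sign changes also become AEs. Some may be coded to Investigations. They would be counted as laboratory findings only if AEs are not matched to a laboratory result. The AE items in Protocol 11.1.2 (name, dates, severity, seriousness, action, treatment, outcome, causality) do not identify a laboratory parameter, and the SAP states no matching rule.

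5. **What does not depend on the rule.** Under SAP 2.6, an AE recorded as a diagnosis stays in the treatment-emergent AE tables by SOC and preferred term. It also stays in the by-subject AE listings with its verbatim term and dates. The laboratory value stays in the out-of-range listing and the panel listings. The shift tables run from baseline to last on treatment and are unaffected. No efficacy analysis or test uses the flag.

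6. **Size.** The number of results in P but not in S depends on how sites word events and how those events are coded. The documents give neither, so no estimate or range can be offered.

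**The case against.** The strongest case for leaving the rule alone has four parts.

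- **Sites may record the finding itself.** Protocol 8.3.3 can be read as asking for the abnormal result to be the AE, and 11.1.1 counts an abnormal laboratory finding as a kind of sign. The diagnosis preference in 11.1.2 is a general rule with a fallback. An isolated abnormal value with no diagnosis can be entered as the finding, and the filter would then presumably catch it. This stands. A reader might infer that the protocol orders laboratory abnormalities to be turned into diagnoses, but it does not. It states a preference, and the SAP rule fails where that preference is followed.

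- **Nothing is lost from the safety data.** This also stands. A reader might infer that every laboratory AE named as a diagnosis disappears. The AEs and the values remain in the other outputs. What is missing is the flag and the entry in one listing, and only for AEs coded outside Investigations.

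- **Coding outside Investigations is not shown in the documents.** This is correct, and it is carried as an assumption. It need hold only for some terms for the listing to be incomplete.

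- **Matching rules may exist elsewhere.** SAP Appendix E places detailed derivations in separate dataset specifications, which are not available here. A reader might infer that vital-sign AEs will be listed as laboratory results. That follows only if no matching is done, and the SAP's silence does not prove it. Matching would not cure under-flagging, however, because an AE removed by the SOC filter is never offered for matching.

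**Conclusion.** The point holds as a minor one. The SAP states a rule that, followed as written, can give an incomplete listing of clinically significant laboratory results, and it narrows the protocol's definition without saying so in section 4. This is more than missing detail, because the stated restriction itself is what can make the listing wrong.

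The conclusion rests on two things: at least some sites follow the diagnosis preference for laboratory abnormalities, and at least some of those diagnoses are coded outside Investigations. The effect is confined to the significance flag and one descriptive listing, and its size is unknown. Over-inclusion of non-laboratory AEs is a possibility to be closed off, not an established error.

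**What to change.** Remove the SOC restriction from SAP 2.6 and replace it as follows:

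1. If the Investigator's assessment of each out-of-range result is collected, take clinical significance from it directly. The eCRF is not among the documents, so this needs checking first.
2. If it is not collected, carry out a blinded review of AE terms across all SOCs before unblinding, matching each relevant AE to the out-of-range laboratory parameter and date. Matching also keeps vital-sign and other non-laboratory AEs coded to Investigations out of the listing.
3. List the derivation in SAP section 4.

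The cost is SAP wording and a small amount of extra blinded review. The SAP already plans blinded work of this kind: reasons for stopping treatment in section 3.2, and protocol deviations classified before unblinding in section 3.4.

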3. DATA HANDLING

3.1 Baseline and Study Visits

Visits for all analyses will be as recorded on the electronic Case Report Forms. Baseline will be the latest of the non-missing values prior to receiving treatment. The following analysis windows will be used for all efficacy and safety data:

Visit	Target Day	Beginning of the Window	End of the Window
██████████	████	████	████
██████████	████	████	████
██████████	████	████	████
██████████	████	████	████
██████████	████	████	████

Note: All days are relative to the date of first treatment application.

If there is more than 1 assessment of the same data in the same window, then the latest assessment within the window will be used for analysis in the tables.

3.2 Missing Data

For the primary analysis, the MI method will be the primary method for dealing with missing data. LOCF and OC analyses will be done as sensitivity analyses. For the count secondary endpoints, MI will be used; for the dichotomous secondary endpoints and the aBCCdex endpoint, LOCF will be used.

For the MI model, 100 imputations will be generated using PROC MI of SAS. Fully conditional specification (FCS) model using the regression method will be used with the change from the last time-point in the number of SEBs at prior post-baseline visits, number of BCCs that are not SEBs at baseline, prior HHI therapy, gender, geographic region, and age ██████████ as covariates to impute any missing data including missed visits and missing data due to dropouts. Missing data of subjects on Patidegib who discontinued due to intercurrent events of AEs, use of a prohibited concomitant medication or lack of efficacy (determined during blind data review of the reasons for study treatment stopped) will be imputed based on vehicle and imputed based on randomized treatment for remaining subjects to estimate the treatment effect if patients would continue to be treated for the entire study unless forced to discontinue treatment due to an AE or lack of efficacy or used a prohibited concomitant medication. If there is a problem with imputing based on the full model, then region will be dropped. The ROUND and MINIMUM options will be utilized to ensure imputed values are non-negative integers. The seed to be used is 20180330. The results from the MI will then be used to derive the number of nSEBs at each timepoint and then analyzed using the primary analysis model. The results of the 100 analyses will be transformed into a normal statistic and combined into a single analysis using

Pelle-926-301 Statistical Analysis Plan

17 June 2020

PROC MIANALYZE. The Wilson-Hilferty transformation (Wilson and Hilferty, 1931) will be utilized to combine the results of the 100 non-parametric Rank ANCOVA analyses.

For the primary and secondary efficacy endpoints related to number of nSEBs, a nSEB that was first reported at or prior to Month 12 will be counted in the endpoint. The lesion will be considered a nSEB at the time it was first reported clinically even if it is biopsied and confirmed later.

The following additional sensitivity analyses utilizing Negative Binomial regression will be provided for the primary endpoint to explore the space of plausible missing data assumptions:

- An MI analysis using the model for the primary imputation but by vehicle for all subjects who dropped out, irrespective of the cause, and MI by randomized treatment for the remaining subjects.
- A tipping point analysis which will impute the results at the months prior to the analysis using the same model for the primary imputation will be performed if and only if the result of the primary endpoint is significant. One hundred imputations will be generated using PROC MI of SAS. The imputation at Month 12 will be imputed using the MNAR ADJUST statement within SAS to shift the imputed values for the increase in nSEBs for subjects randomized to the Patidegib arm by different values until the p-value changes from significant to non-significant. The seed to be used is 20180330.

In order to classify a medication as prior or concomitant or classify an AE as treatment-emergent or not, missing or partial dates will be imputed. Please see Appendix D for full details of the imputation of missing/partial dates.

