2.2 Sample Size Determination

In the UK Phase 2 study of patients with Gorlin syndrome (Pelle-926-201), the mean number of nSEBs (erroneously stated in the protocol as mean number of new BCCs in the Section on Sample size determinations) at 6 months was █ in the Patidegib Topical Gel, 2%, group with an SD of █, and a mean of 1.4 in the Vehicle Gel group with a SD of 1.52. The effect size was 0.81. Because the current trial is longer, more conservative assumptions are made. It is assumed that at 6 months, the mean number of nSEBs in the Patidegib Topical Gel, 2%, group will be 0.6, with an SD of █, while at 6 months the mean and SD in the Vehicle Gel group will be the same as in the Phase 2 study at 6 months for an effect size of 0.63. At 12 months, it is assumed that the means and SDs will be twice those of 6 months. With these assumptions, █ subjects in the Patidegib Topical Gel, 2%, group and 63 in the Vehicle Gel group (for a total of █ subjects) will give >90% power for a 2-sided 0.05 level statistical significance. To account for a 16% drop-out rate, approximately 150 subjects will be randomized.

The primary endpoint of number of qualifying nSEBs per subject by Month 12 may be affected by follow-up time. Based on the UK Phase 2 study (Pelle-926-201), it is projected that the power calculated above will be substantially similar unless marked differences are seen between the treatment arms in follow-up time. Sample size was calculated based on a Wilcoxon-Mann-Whitney test which is conservative if the underlying distribution is Negative Binomial.

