2.5.2 Secondary Efficacy Analysis

The secondary efficacy endpoints are:

1. The number of new BCCs that develop from Baseline to Month 12.
2. The proportion of subjects developing ≥ 2 facial nSEB(s) by Month 12.
3. The proportion of subjects developing ≥ 1 facial nSEB(s) by Month 12.
4. The number of qualifying nSEBs per subject at Month 9 (defined as the number of qualifying nSEBs per subject by Month 9).
5. The number of qualifying nSEBs per subject at Month 6 (defined as the number of qualifying nSEBs per subject by Month 6).
6. Advanced BCC Index (aBCCdex) change in lesion score from Baseline to Month 12.

The number of new BCCs that develop from Baseline to Month 12 will be analyzed using a negative binomial regression to compare treatment groups with number of BCCs at Baseline, Age (█████ years), gender, prior HHI therapy, and geographic region strata (North America, Europe) as covariates. Secondary endpoints that are based on number of nSEBs will be analyzed similar to the primary endpoint. The proportion of subjects with at least 2 nSEB lesions and the proportion of subjects with at least 1 nSEB lesion will be analyzed using a logistic regression to compare treatment groups with number of BCCs that are not SEBs at Baseline, Age (█████ years), gender, prior HHI therapy, and geographic region strata (North America, Europe) as covariates. Change in aBCCdex scores will be analyzed using an ANCOVA model with treatment group as a main effect, the corresponding baseline aBCCdex scale score, prior HHI therapy, gender, age █████ old), and geographic region strata as covariates. Please see Appendix A for the scoring instructions for the aBCCdex lesion scale score. A box plot of the number of new BCCS per subject over time will be presented. An analysis of the number of new BCCs by Month 12 in the PP Population using OC will be provided as a sensitivity analysis.

The secondary endpoints will be tested sequentially in the order above using a gatekeeping strategy with type-1 error of 0.05 at 12 months. If and only if the primary endpoint is statistically significant will the secondary efficacy endpoints be tested using the gate-keeping procedure.

All efficacy assessments (secondary and exploratory endpoints) will be summarized descriptively by treatment group and visit.

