2.5.3 Exploratory Endpoints

The exploratory endpoints are:

1. Time to first nSEB.
2. The proportion of SEBs that undergo clinical resolution at Month 12.
3. The number of BCC surgeries from Baseline to Month 12.
4. Change in aBCCdex Worry About Future Lesions scale score from Baseline to Month 12.
5. Change in aBCCdex Mental Health scale score from Baseline to Month 12.
6. Change in aBCCdex Social/Relationships scale score from Baseline to Month 12.
7. Change in aBCCdex Life Impact scale score from Baseline to Month 12.
8. Change in Skindex-16 subscales (Symptoms, Emotions, and Functioning) from Baseline to Month 12
9. Change in Dermatology Life Quality Index (DLQI) total score from Baseline to Month 12
10. Shift in EuroQol (Quality of Life) using 5 levels (EQ-5D-5L) from Baseline to Month 12
11. Change in EQ-5D-5L Visual Analog Scale (VAS) from Baseline to Month 12

The time to first nSEB, defined as the date of first new SEB – date of randomization + 1, will be summarized using the Kaplan-Meier method. Subjects who do not develop an nSEB will be censored at the date of last tumor assessment, regardless of whether or not the subject was still on treatment. A Kaplan-Meier plot will also be provided.

The proportion of SEBs that undergo clinical resolution at Month 12 (or last assessment utilizing LOCF imputation) and the number of BCC surgeries will be summarized descriptively.

Change in Skindex-16 subscale scores and the DLQI total score will be summarized descriptively by visit. Please see Appendix B for the Skindex-16, and Appendix C for the DLQI.

A separate analysis plan for the pharmacokinetic data will be provided.

A shift table will be presented for changes from baseline of the EQ-5D-5L dimension scores. Additionally, the VAS Scores will be summarized descriptively by visit.

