4. CHANGES FROM THE PROTOCOL

This section highlights text in the SAP that overrides the cited text in the protocol.

The protocol (Section 8.2.1) refers to an Imaging Review Charter. In actuality this is an Imaging Review Work Instruction.

In the section on Sample Size Determination (Section 12.9) the protocol states ‘mean number of new **BCC** lesions at 6 months was 0.42’ instead of ‘mean number of new **SEB** lesions at...’

The secondary endpoints for the number of nSEBs at Months 6 and 9 were clarified to reflect that they are “by Month” 6 or 9 to bring these endpoints in line with the primary endpoint. Exploratory endpoints for the time to first nSEB, Skindex-16, DLQI, and EQ-5D-5L questionnaires were added.

The primary endpoint analysis distributional assumption was changed from Poisson to Negative Binomial based on FDA and EMA feedback, however the primary endpoint remains unchanged.

Pelle-926-301 Statistical Analysis Plan

17 June 2020

The interim analysis will no longer be performed based on EMA Scientific Advice, dated 26Mar2020, and FDA advice during a Type B Meeting held on 11May2020 recommending that the interim analysis should not be conducted; only a final analysis will be performed at an alpha level of 0.05 instead of 0.045 (both primary and secondary endpoints).

Laboratory test results will be summarized as change from baseline to last result on treatment instead of at each visit to provide a more concise, medically relevant summary.

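### SAP 3.2 multiply imputes the lesion counts but gives only LOCF for the ranked ≥2 and ≥1 lesion proportions taken from those counts, against the protocol's rule that multiple imputation is primary

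*SAP*

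**What the plan says.** **SAP.** Section 3.2 assigns MI to the primary endpoint and the count secondary endpoints. The same sentence continues: "for the dichotomous secondary endpoints and the aBCCdex endpoint, LOCF will be used". The imputation is used to derive nSEB counts at each timepoint, so Month 12 counts exist in all 100 imputed data sets. The count rule depends on why treatment stopped: "Missing data of subjects on Patidegib who discontinued due to intercurrent events of AEs, use of a prohibited concomitant medication or lack of efficacy" are imputed from vehicle, and all other missing data by randomized arm.

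In Section 2.5.2 the proportions with ≥2 and ≥1 facial nSEBs are second and third on the list, and "The secondary endpoints will be tested sequentially in the order above using a gatekeeping strategy". The additional missing-data analyses in Section 3.2 "will be provided for the primary endpoint to explore the space of plausible missing data assumptions"; the proportions get none.

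**Protocol.** Sections 12, 12.6.2 and 12.7.6 make MI the primary method, with LOCF and observed case as sensitivity analyses. The Synopsis says that secondary endpoints based on new BCC or nSEB counts follow the primary analysis, and it names both proportions among them. Section 7.3 asks for evaluations at early termination. Section 7.4 says that nothing more can be collected after withdrawal.

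**The concern.** Each proportion is the Month 12 count cut at a threshold. Using one missing-data rule for the count and another for its threshold makes ranked tests on the same data answer different questions. For a cumulative count, LOCF is equivalent to assuming that no lesion appears after the exit assessment. It also bypasses the vehicle-based rule, so a patidegib subject who stops for an adverse event while lesion-free stays a success in the proportion tests but is imputed from vehicle in the count tests.

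LOCF can only hold or lower each subject's count, so it pulls both proportions down in each arm. The effect on the comparison then depends on which arm loses more subjects, and when. At stake are the effect estimates for two ranked endpoints and the chance of passing them.

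**Working it through.** **Inputs.** SAP 2.2: 6-month vehicle mean 1.4, SD 1.52; patidegib mean 0.6; effect size 0.63; 16% dropout; about 150 randomized. Protocol Synopsis: patidegib SD 0.94; 126 evaluable. For Month 12, SAP 2.2 states: "At 12 months, it is assumed that the means and SDs will be twice those of 6 months". This gives vehicle 2.8 (SD 3.04) and patidegib 1.2 (SD 1.88). These are nSEB values; the documents give none for new BCCs.

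**Reproducing the plan.** Pooled SD = √((1.52² + 0.94²)/2) = 1.264, and 0.8/1.264 = 0.63. Then 126/(1 − 0.16) = 150. Both match.

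**Assumptions of this check.** Negative binomial counts with mean proportional to time; 75 per arm; exits spread equally over Months 3, 6 and 9, each with an exit assessment. The documents give only the overall 16%, so every split between arms is assumed.

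**Dispersion.** (SD² − mean)/mean²: vehicle (9.2416 − 2.8)/7.84 = 0.82; patidegib (3.5344 − 1.2)/1.44 = 1.62.

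**Proportion at Month 12, and the average of its values at Months 3, 6 and 9**

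| | Month 12 | Average at exit |
|---|---|---|
| Vehicle ≥1 | 0.7662 | 0.5786 |
| Patidegib ≥1 | 0.4864 | 0.3284 |
| Vehicle ≥2 | 0.5679 | 0.3321 |
| Patidegib ≥2 | 0.2772 | 0.1390 |

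**LOCF proportion** = (1 − d) × P(Month 12) + d × P(exit), where d is the dropout fraction. Example, ≥1 with 16% in both arms: patidegib 0.84 × 0.4864 + 0.16 × 0.3284 = 0.461; vehicle 0.84 × 0.7662 + 0.16 × 0.5786 = 0.736; odds ratio 0.307.

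| Dropout, patidegib/vehicle | ≥1: patidegib vs vehicle | OR | ≥2: patidegib vs vehicle | OR |
|---|---|---|---|---|
| None | 48.6% vs 76.6% | 0.289 | 27.7% vs 56.8% | 0.292 |
| 16/16 | 46.1% vs 73.6% | 0.307 | 25.5% vs 53.0% | 0.303 |
| 20/12 | 45.5% vs 74.4% | 0.288 | 25.0% vs 54.0% | 0.284 |
| 24/8 | 44.8% vs 75.1% | 0.269 | 24.4% vs 54.9% | 0.265 |
| 8/24 | 47.4% vs 72.1% | 0.348 | 26.6% vs 51.1% | 0.347 |

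**No drug effect.** The spurious gap is (difference in dropout) × (Month 12 minus exit proportion). At 24/8 it is 0.16 × (0.7662 − 0.5786) = 3.0 points for ≥1 and 0.16 × (0.5679 − 0.3321) = 3.8 points for ≥2, both in favour of patidegib. Taken alone, the two-sided error is 6.9% (≥1) and 7.0% to 8.2% (≥2, depending on the test), against 4.6% to 5.6% with equal dropout. At 8/24 the gaps reverse. Two variations at 24/8: using the 6-month dispersion (0.46) for early exits gives 2.4 and 3.6 points; if a quarter of exits have no post-baseline assessment, the gaps are 5.3 and 5.1 points.

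**Subjects affected.** Of 12 patidegib exits (16% of 75), 12 × (0.4864 − 0.3284) ≈ 1.9 would be lesion-free under LOCF but have ≥1 lesion by Month 12 under own-arm imputation.

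**Does the SAP's own draw repair this?** The SAP uses regression draws and says: "The ROUND and MINIMUM options will be utilized to ensure imputed values are non-negative integers". In simulation with no drug effect and 16/16 dropout, the bias per arm in points was:

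| Method | ≥1 | ≥2 |
|---|---|---|
| LOCF | −3.1 | −3.7 |
| Rounded regression draws (two readings of the minimum option) | +1.4 to +2.7 | +1.6 to +3.6 |
| Predictive mean matching | +0.4 | +0.3 |

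Under the planning effect at 24/8, the bias in the ≥1 arm difference was −2.3 points for LOCF, +2.8 to +5.4 for rounded draws and +0.5 for matching. Thresholding the rounded draws would therefore replace one bias with another.

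**The case against.** **The rule is explicit and pre-specified.** That is so, and the protocol's phrase about following the primary analysis cannot by itself fix the imputation method, since Section 12.6.2 uses logistic regression for the proportions. But Section 12.6.2 describes those logistic analyses and then restates that MI is primary and LOCF a sensitivity analysis. The split inside SAP 3.2 also remains whichever protocol version applies.

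**Non-declaration.** A reader might infer that the SAP made this change without declaring it, because Section 4 begins "This section highlights text in the SAP that overrides the cited text in the protocol" and does not mention it. The documents do not support that. Section 4 answers a different protocol version: it cites sample size as Section 12.9 (12.8 in the supplied text), corrects an imaging charter reference that the supplied text does not contain, moves from Poisson to a negative binomial model already in the supplied text, and cancels an interim analysis that the supplied text does not have. The missing-data text of that version is not available. The SAP also ranks nSEB proportions where the supplied protocol ranks new-BCC proportions. What stands is that SAP and current protocol disagree and must be reconciled.

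**The SAP has other views of these data.** SAP 2.5.1 plans a histogram of subjects by nSEB count over time, 2.5.2 plans summaries by visit, and 2.5.3 a Kaplan-Meier analysis in which "Subjects who do not develop an nSEB will be censored at the date of last tumor assessment". These are useful, but all are descriptive. None is an inferential sensitivity analysis of either proportion to missing data.

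**The larger effects rest on assumed imbalance.** This stands. Equal dropout works mildly against patidegib, and a 20/12 split leaves the odds ratios almost unbiased.

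**Conclusion.** The point holds as an inconsistency that should be fixed before unblinding, not as a threat to the primary result. Two ranked endpoints rest on a single missing-data method that differs from the one used for the counts they come from, departs from the current protocol's rule, and has no inferential check.

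The size is modest if dropout is balanced or mildly unbalanced: odds ratios of 0.28 to 0.31 against true values of 0.289 and 0.292. An assumed imbalance of 16 points moves them to about 0.27 or 0.35. These figures rest on the nSEB planning values, negative binomial counts and assumed exit timing.

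A reader might infer that LOCF favours patidegib or inflates the trial's false-positive rate. Neither follows. The direction depends on which arm loses more subjects, and that is unknown. The proportions are tested only after MI-based tests succeed, so trial-level type I error is not inflated: with no drug effect and 24/8 dropout, the simulated chance that the primary and the ≥2 test are both significant in favour of patidegib was 1.5%.

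**What to change.** Before unblinding, make MI primary for both proportions, for whichever lesion type the final endpoint uses:

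- Derive the ≥1 and ≥2 indicators from the imputed Month 12 counts, under the same vehicle/own-arm rule as the counts.
- Fit the planned logistic model in each of the 100 data sets and combine with PROC MIANALYZE.
- Keep LOCF and observed case as sensitivity analyses, as the protocol has them.
- Draw the increments as counts, for example by predictive mean matching, rather than by rounding regression draws. Use the same draws for the count endpoints, so that all ranked lesion tests share one set of imputations.

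The cost is a SAP edit and some programming, with no new data, visits or subjects. The real downside is that the draw method for the primary count changes too, so it must be settled before unblinding.

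Minimum alternative: keep LOCF as primary, state and justify it against the current protocol, and add an MI sensitivity analysis with count-valued draws for both proportions.
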